#### 7.6.4. Subgroup Analyses

Subgroup analyses to be performed for the primary and key secondary endpoints based on the FAS are presented in Table 5.

Subgroup	Categories
Randomization stratification factor (per IXRS): Baseline Hb concentration	≤9.0 g/dL; 9.1-10.0 g/dL
Randomization stratification factor (per IXRS): Thalassemia genotype	α-thalassemia/HbH disease; β-thalassemia
Age at screening	<35 years; ≥35 years
Sex	Male; Female
Race	Asian; Black or African American; White; other (other includes American Indian or Alaska Native, Native Hawaiian or other Pacific Islander, multiracial, unknown, and not reported)
Geographical region	North America and Europe; Asia-Pacific; rest of the world

Table 5: Si	ubgroup Analyses f	for the Primary	and the Key Seco	ondary Endpoints
-------------	--------------------	-----------------	------------------	------------------

Efficacy analyses in subgroups will be purely exploratory and are intended to evaluate the consistency of treatment effect. If there is a low number of subjects within a category ( $\leq 10\%$  of the subjects in the FAS), the categories will be pooled (if 3 or more categories are prespecified for the subgroup) or the subgroup will not be analyzed (if only 2 pre-specified categories in the subgroup).

For each category within each subgroup the following unstratified analyses will be performed and presented in a forest plot, separately for the primary endpoint and each of the key secondary endpoints:

- Hb response will be summarized for each treatment arm (number of responders and response rate), along with the 95% exact CI using the Clopper-Pearson method. The difference in response rates between the mitapivat arm and the placebo arm will be summarized together with the 95% CI based on the exact Clopper-Pearson confidence limits.
- Each of the key secondary endpoints will be summarized for each treatment arm using LS means, and the difference between the mitapivat arm and the placebo arm will be presented with the associated 95% CI based on the ANCOVA model described in Section 7.6.2.1 and Section 7.6.2.2 without considering the randomization stratification factors as covariates.

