10.4.2.3. Subgroup Analyses

Hemoglobin response rate will be summarized for subgroups defined by each randomization stratification factor. Within each subgroup, Hb response rate will be summarized by treatment arm, and the difference in Hb response rate between the mitapivat arm and the placebo arm will be estimated (difference in Hb response rate and 95% CI) using an unstratified method.

Hemoglobin response may be summarized for other subgroups prespecified in the SAP.

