## 6.2. Sample Size Determination and Decision Rules

#### 6.2.1. Sample Size Determination

The following statistical hypothesis will be tested to address the primary objective:

 $H_{01}$ :  $p_{t1} - p_{c1} = 0$  vs  $H_{11}$ :  $p_{t1} - p_{c1} \neq 0$ 

where  $p_{t1}$  and  $p_{c1}$  are the proportion of subjects with a Hb response in the mitapivat arm and placebo arm, respectively.

Assuming an Hb response rate of 10% in the placebo arm, 171 subjects (114 subjects randomized to mitapivat and 57 subjects randomized to placebo) are needed to provide a 95% power to detect an increase in Hb response rate from 10% in the placebo arm to 35% in the mitapivat arm based on a 2-sided significance level of 0.05.

Given the large variability of Hb concentration in patients with anemia, the SD of change from baseline can be as high as 1.3 g/dL (Kalantar-Zadeh and Aronoff, 2009). Assuming no changes in Hb concentration in subjects receiving placebo, approximately 10% of subjects could achieve an Hb response simply because of the variability in Hb concentration measurements. Therefore, a 10% Hb response rate is being assumed for the placebo arm.

The assumption of a 35% Hb response rate was informed by the results from Study AG348 C-010. As of 20 August 2020, 70% (14/20 overall, 10/15 in those with  $\beta$ -thalassemia, and 4/5 in those with  $\alpha$ -thalassemia) subjects achieved a  $\geq 1.0$  g/dL increase in average Hb concentration from Week 12 through Week 24 compared with baseline. Considering a more heterogeneous population in this large, double-blind, Phase 3 study and a commonly noted decrease in efficacy between Phase 2 and Phase 3 studies, a 35% response rate for mitapivat arm is deemed to be a reasonable assumption.

Additionally, the following statistical hypotheses will be tested to address the key secondary objectives:

```
\begin{split} H_{02}: \mu_{t1} - \mu_{c1} &= 0 \ \text{vs} \ H_{12}: \ \mu_{t1} - \mu_{c1} \neq 0 \\ H_{03}: \mu_{t2} - \mu_{c2} &= 0 \ \text{vs} \ H_{13}: \ \mu_{t2} - \mu_{c2} \neq 0 \end{split}
```

where

- $\mu_{t1}$  and  $\mu_{c1}$  are the mean change from baseline in average FACIT-Fatigue subscale score from Week 12 through Week 24 in the mitapivat arm and placebo arm respectively
- μt2 and μc2 are the mean change from baseline in average Hb concentration from Week 12 through Week 24 in the mitapivat arm and placebo arm, respectively

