## 7.6.1.1. Primary Analyses

The primary endpoint of Hb response will be tested using the Mantel-Haenszel stratum weighted method adjusting for randomization stratification factors. The proportion of subjects who achieved a Hb response will be summarized for each treatment arm. The adjusted difference in Hb response rate between the mitapivat arm and placebo arm, along with the 95% CI and the 2-sided p-value, will be provided.

In addition, for subjects who achieve an Hb response, mean Hb concentration increase and duration of Hb response will be summarized by treatment arm. For subjects who achieve Hb response, duration of Hb response will be calculated as the number of days from start of Hb response through the date of loss of Hb response, where:

- Start of Hb response is defined as the earliest date on or after the 'reference date' (as defined in Section 6.3.4.1) with Hb change from baseline  $\geq 1.0 \text{ g/dL}$
- Loss of Hb response is defined to have occurred on the first date with Hb change from baseline <1.0 g/dL after the last assessment with Hb change from baseline  $\ge 1.0 \text{ g/dL}$

• For subjects who do not have loss of Hb response, the duration of Hb response will be censored at the end of the 24-week Double-blind Period.

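### SAP 7.6.4 bases the subgroup confidence interval for the difference in Hb response rates on Clopper-Pearson limits, a one-proportion method that does not define an interval for a difference

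*SAP*

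**What the plan says.** SAP 7.6.4 plans unstratified analyses within each subgroup category, shown in a forest plot. For Hb response it makes two statements about intervals:

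- Each arm's response rate is reported "along with the 95% exact CI using the Clopper-Pearson method".
- The difference in rates between arms "will be summarized together with the 95% CI based on the exact Clopper-Pearson confidence limits".

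Protocol 10.4.2.3 says only that the subgroup difference "will be estimated (difference in Hb response rate and 95% CI) using an unstratified method". Neither document names a two-sample method for this difference or gives a rule for combining the two arms' limits.

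Two further statements bound the issue. The SAP calls the subgroup efficacy analyses "purely exploratory and are intended to evaluate the consistency of treatment effect". The primary endpoint itself "will be tested using the Mantel-Haenszel stratum weighted method adjusting for randomization stratification factors", which makes no use of Clopper-Pearson limits.

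**The concern.** Clopper-Pearson inverts the exact binomial test for one proportion. It yields a lower and an upper limit for one rate, so the first statement is sound. A difference of two independent rates is a different quantity, and the second statement does not fix an interval for it. A programmer could subtract the limits crosswise, combine them by square-and-add, or assume that an exact two-sample interval was meant. All three fit the wording loosely, and they do not give the same numbers.

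At stake is the reading of the forest plot, whose purpose is to show whether the effect is consistent across subgroups. Error bars that are too wide make a real inconsistency harder to see and can make a real effect look unsupported in a subgroup. The choice between constructions would also be left open in a plan meant to settle it before unblinding.

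**Working it through.** **Inputs.** From SAP 6.2.1: 114 v 57 subjects (2:1), response rates 35% v 10%, two-sided 0.05, and a Phase 2 response rate of 70%. From SAP 7.6.4: a category with at most 10% of the FAS is pooled or not analysed. Since 0.10 × 171 = 17.1, the smallest category analysed has 18 subjects, or 12 v 6 at 2:1. The documents give no expected subgroup sizes, so 57 v 28, 36 v 18, 20 v 10 and 12 v 6 are assumptions.

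**The plan's own figure.** The plan gives no figure for the subgroup interval. For the same endpoint it states 95% power with 171 subjects. The pooled rate is (114 × 0.35 + 57 × 0.10)/171 = 0.267. The null SE is √[0.267 × 0.733 × (1/114 + 1/57)] = 0.0717. The alternative SE is √[0.35 × 0.65/114 + 0.10 × 0.90/57] = 0.0598. Then z = (0.25 − 1.96 × 0.0717)/0.0598 = 1.83, so power is 96.6%. Fisher's exact test, by enumeration, gives 96.1%. The stated power is met.

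**Formulas.** Let the arm rates be p₁ and p₂, with 95% limits (l₁, u₁) and (l₂, u₂), and D = p₁ − p₂.

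- Direct subtraction: l₁ − u₂ to u₁ − l₂.
- Square-and-add: D − √[(p₁ − l₁)² + (u₂ − p₂)²] to D + √[(u₁ − p₁)² + (p₂ − l₂)²].
- Newcombe: square-and-add with Wilson limits in place of Clopper-Pearson limits.
- Miettinen-Nurminen: inversion of the two-sample score test.

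Write the two distances on one side as a and b. Subtraction uses a + b and square-and-add uses √(a² + b²). Subtraction is therefore never narrower, and it is √2 = 1.41 times as wide when a = b.

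**One data set, 20/57 v 3/28.** Here p₁ = 0.351, p₂ = 0.107 and D = 0.244. The Clopper-Pearson limits are 0.229 to 0.489 and 0.023 to 0.282.

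- Subtraction: 0.229 − 0.282 = −0.05; 0.489 − 0.023 = 0.47.
- Square-and-add: 0.244 − √(0.122² + 0.175²) = 0.03; 0.244 + √(0.138² + 0.084²) = 0.41.
- Newcombe: 0.05 to 0.39.
- Miettinen-Nurminen: 0.05 to 0.40.

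Subtraction includes zero; the other three exclude it.

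**Coverage and mean width.** These come from full enumeration of both binomial distributions at the four assumed sizes. At 35% v 10%:

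| Interval | Coverage | Width / Newcombe | Width / Miettinen-Nurminen | Mean width, 57 v 28 | Mean width, 12 v 6 |
|---|---|---|---|---|---|
| Subtraction | 99.8% to 99.9% | 1.48 to 1.50 | 1.41 to 1.46 | 0.50 | 1.09 |
| Square-and-add, Clopper-Pearson | 97.1% to 98.8% | 1.08 to 1.18 | 1.07 to 1.11 | 0.37 | 0.85 |
| Newcombe | 95.0% to 96.7%, jointly with Miettinen-Nurminen | 1 | – | 0.34 | 0.73 |
| Miettinen-Nurminen | as above | – | 1 | 0.34 | 0.77 |

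At 70% v 10%, the width ratios to Newcombe are 1.51 to 1.57 for subtraction and 1.09 to 1.18 for square-and-add.

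**Effect on the display.** At 57 v 28 and 35% v 10%, the interval lies wholly above zero in 34% of trials under subtraction, 67% under square-and-add and 73% under Newcombe. The square-and-add interval always lies inside the subtraction interval, so the two readings disagree about zero in 67% − 34% = 33% of trials.

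**The case against.** The SAP says the interval is based on Clopper-Pearson limits, which is looser than saying it is computed by that method. Square-and-add is a legitimate way to build an interval for a difference from two such intervals. On that view the defect is an unstated combining rule, and the largest figures above come from the least favourable reading, which the SAP never states.

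If an exact two-sample interval was meant, little would change. For 20/57 v 3/29, the exact unconditional score interval is 0.035 to 0.410, square-and-add of Clopper-Pearson limits is 0.038 to 0.408, and Newcombe is 0.052 to 0.394. (Subtraction gives −0.044 to 0.467.)

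The suggested replacements are not perfect either. At 70% v 10%, Miettinen-Nurminen covers 94.2% at 57 v 28 and Newcombe 94.4% at 36 v 18, whereas both Clopper-Pearson constructions stay above 95%. Finally, the display is exploratory, no decision rule uses it, and the error is towards caution.

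Much of this stands. The subtraction figures are the extreme of the readings computed, the milder readings differ from a score interval by modest amounts, and the consequence is narrow. None of it supplies the missing definition. If several constructions fit the sentence and they disagree about zero in a third of trials at 57 v 28, the sentence has not specified an interval. If an exact two-sample method was intended, the SAP has named the wrong one. The shortfalls of the score-type intervals below 95% are under one percentage point.

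**Conclusion.** The point holds. The method named for the subgroup difference is a method for another quantity, and no other part of the protocol or SAP repairs it. At 35% v 10%, the plotted intervals would be mildly conservative under square-and-add (97.1% to 98.8% coverage, 8% to 18% wider than Newcombe) or strongly so under subtraction (99.8% to 99.9%, 48% to 50% wider).

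These figures rest on assumed subgroup sizes, 2:1 allocation within each subgroup and the planning rates. The exact unconditional reading was worked only for single data sets, not for coverage.

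The reach is limited to the exploratory Hb response forest plot. Point estimates, per-arm rates and their intervals, the Mantel-Haenszel primary test, type I error, sample size and the ANCOVA-based subgroup plots are unaffected. It should be corrected, but it does not threaten the trial's main conclusions.

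**What to change.** In SAP 7.6.4, keep Clopper-Pearson for the per-arm response rates only. For the difference, name one unstratified two-sample 95% interval: the Miettinen-Nurminen score interval or the Newcombe interval, or an exact unconditional score interval if an exact method is required.

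Protocol 10.4.2.3 asks only for an unstratified method, so any of these complies and no protocol amendment is needed. The cost is one SAP sentence, settled before unblinding, and a standard software option.

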# 7.7. Safety Analyses

Safety data from the double-blind on-treatment period (Section 6.3.5) will be summarized based on the safety analysis set, by treatment arm.

Safety data from the OLE on-treatment period alone (Section 6.3.5) will be summarized separately based on the OLE analysis set, by treatment arm and overall.

## 7.7.1. Adverse Events

Treatment-emergent adverse events (TEAEs) are AEs with a first onset date during the ontreatment period or worsening from baseline. All summaries described below will be based on TEAEs, if not otherwise specified.

All AEs will be listed by subject and AEs with onset outside of the on-treatment period will be flagged in the listings. Unless otherwise specified, TEAEs will be summarized according to the latest version of MedDRA by SOC and/or PT, severity (based on CTCAE v4.03 grading), seriousness, and relation to study treatment in decreasing frequency based on the frequencies observed for the mitapivat arm.

Each subject will be counted only once within each SOC or PT. If a subject experiences multiple TEAEs under the same PT within a SOC for the same summary period, only the TEAE assessed as related or with the worst severity, as applicable, will be included in the summaries of relationship and severity. If a subject has TEAEs with missing and non-missing grades, the maximum of the non-missing grades will be displayed. No imputation of missing grades will be performed.

The following will be summarized:

• TEAEs by SOC and PT

- TEAEs by SOC, PT, and worst grade
- Most common TEAEs and Grade ≥3 TEAEs by PT; these will include TEAEs (any grade) reported in ≥10% of subjects in either treatment arm or Grade ≥3 TEAEs reported in ≥5% of subjects in either treatment arm. These thresholds may be changed based on the observed data without an amendment to this SAP.
- Treatment-related TEAEs, by SOC and PT
- Treatment-related TEAEs, by SOC, PT, and worst grade
- Grade  $\geq$ 3 TEAEs, by SOC and PT
- Treatment-related Grade  $\geq$ 3 TEAEs, by SOC and PT
- Serious TEAEs, by SOC and PT
- Treatment-related serious TEAEs, by SOC and PT
- TEAEs leading to discontinuation of study drug, by SOC and PT
- TEAEs leading to interruption of study drug, by SOC and PT
- TEAEs leading to dose reduction, by SOC and PT
- TEAEs leading to death, by SOC and PT
- Treatment-related TEAEs leading to death, by SOC and PT

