- ¹ At any time during the study, subjects who discontinue study drug should undergo the recommended dose taper and complete the assessments at the Safety Follow-up visit after administration of their last dose of study drug (ie, including the recommended dose taper). Subjects who withdraw from the study should be encouraged to first undergo the recommended dose taper (Table 4) and complete the Safety Follow-up visit. Subjects who are discontinuing study drug should be monitored for signs of hemolysis and worsening of anemia, as clinically indicated.
- ² The Safety Follow-up visit is to be completed after administration of the last of any dose of study drug (ie, including the recommended dose taper).
- ³ If allowed by local institutional guidelines, and at the discretion of the Investigator and the subject, subjects will have the option to complete study-specific assessments at home instead of in person at the clinical study center. These visits (Investigator Assessment only) will be conducted by the Investigator (or designee) (see Section 8).
- ⁴ After completing the study visit at Week 288, subjects should begin the dose taper.
- ⁵ Pregnancy testing should occur more frequently as clinically indicated (ie, if there is suspicion of pregnancy) or if required by local regulations. A serum or urine pregnancy test will be performed locally for WOCBP at the Safety Follow-up visit.

Η

- ⁸ Vital signs include systolic and diastolic blood pressure, pulse rate, and body temperature. Weight will also be recorded. Vital signs should be measured after 5 minutes of recumbency, and before blood sample collection.
- ⁹ Hematology includes a complete blood count (Hb, HCT, MCHC, MCH, MCV, RBC count, nucleated RBCs, RDW-CV, % reticulocyte count, absolute reticulocyte count, and platelet count) with WBC count and differential (neutrophils, basophils, lymphocytes, and monocytes).
- ¹⁰Clinical chemistry includes albumin, BUN or urea, total calcium, CO₂ or bicarbonate, chloride, creatinine, magnesium, magnesium, phosphorus, potassium, sodium, total protein, and uric acid.
- ¹¹Liver tests include ALP, ALT/SGPT, AST/SGOT, and bilirubin (direct/conjugated, indirect/unconjugated, and total). LDH will also be measured.
- ¹²Lipid panel includes nonfasting HDL-C, LDL-C, total cholesterol, and triglycerides.

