#### 6.3.5. On-Treatment Period

The on-treatment period starts on the date of the start of study treatment and ends 28 days after the end of study treatment (including dose taper period).

Within the on-treatment period, there are two distinct treatment periods:

- Double-blind on-treatment period starts on the date of the start of study treatment and ends
  - 28 days after the end of study treatment, for subjects who discontinue study treatment during the Double-blind Period of the study
  - Before the start of the OLE treatment period, for subjects who continue onto the OLE Period of the study

• OLE on-treatment period applies only to subjects who complete the Double-blind Period of the study, and starts with the first dose of open-label mitapivat in the OLE Period and ends 28 days after the end of study treatment

For subjects who receive mitapivat in the OLE Period, assessments or events occurring on the date of first dose of mitapivat in the OLE Period will be included in the analysis of the data from the double-blind on-treatment period, except for AEs and concomitant medications reported for subjects in the placebo arm which will be included only in the analysis of the data from the OLE on-treatment period.

Data listings will include all assessments and events, with those that occur outside of the on-treatment period flagged.

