### Parameters with CTCAE grades available:

Clinical laboratory test results will be graded according to CTCAE v4.03 as applicable. Grading will be derived based on the numerical thresholds defined by the CTCAE criteria. Non-numerical qualifiers will not be taken into consideration in the derivation of CTCAE grading.

Laboratory test results classified according to CTCAE will be described using the worst grade. For parameters graded with 2 separate toxicity criteria, such as potassium (hypokalemia/hyperkalemia), the toxicities will be summarized separately. Low direction toxicity (eg, hypokalemia) grades at baseline and postbaseline will be set to 0 when the variables are derived for summarizing high direction toxicity (eg, hyperkalemia), and vice versa.

The frequency of subjects with laboratory toxicities during the on-treatment period will be tabulated as follows. The denominator used to calculate percentages for each laboratory test is the number of subjects evaluable for CTCAE grading for that parameter (ie, those subjects for whom a Grade of 0, 1, 2, 3 or 4 can be derived).

- The summary of laboratory parameters by CTCAE grade will include the number and percentage of subjects with Grade 1, 2, 3, 4; Grade 3-4; and Any Grade (Grades 1-4) during the on-treatment period. The highest CTCAE grade during the on-treatment period is considered the worst grade.
- The shift table will summarize baseline CTCAE grade versus worst CTCAE grade during the on-treatment period. The highest CTCAE grade during the on-treatment period is considered the worst grade.
- Newly occurring or worsening laboratory abnormalities (Any Grade, Grade 3-4) during the on-treatment period will also be summarized.

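### Adverse events after stopping study drug cannot be told apart from on-drug events in the TEAE tables, and an on-schedule Safety Follow-up sample on days 29 to 32 misses the laboratory worst-grade and shift tables

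*SAP*

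**What the plan says.** **The named risk.** Protocol 6.1, 6.7 and 7.1 ask sites to taper subjects who stop study drug and to monitor them for acute hemolysis and worsening anemia. The schedule notes repeat this: "Subjects who are discontinuing study drug should be monitored for signs of hemolysis and worsening of anemia, as clinically indicated". Planned stopping at the end of the extension is included: "After completing the study visit at Week 288, subjects should begin the dose taper".

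**The period.** SAP 6.3.5: "The on-treatment period starts on the date of the start of study treatment and ends 28 days after the end of study treatment". The end of study treatment is the last non-zero dose (SAP 6.3.2), so the taper counts as treatment.

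**The adverse event tables.** SAP 7.7.1: "Treatment-emergent adverse events (TEAEs) are AEs with a first onset date during the ontreatment period or worsening from baseline". Each treatment period is summarized as a whole. For the extension, SAP 7.7 says: "Safety data from the OLE on-treatment period alone (Section 6.3.5) will be summarized separately based on the OLE analysis set". Counting is by subject: "Each subject will be counted only once within each SOC or PT". For repeated events under one PT, "only the TEAE assessed as related or with the worst severity, as applicable, will be included in the summaries of relationship and severity".

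**The laboratory tables.** Worst-grade and shift tables use the same period: "The highest CTCAE grade during the on-treatment period is considered the worst grade". Protocol Table 2 puts Safety Follow-up 28 days after the last dose with a window of ±4 days. Hematology, liver tests and LDH are scheduled at that visit.

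**The concern.** The protocol singles out one clinical risk of stopping, and the visible SAP has no output that isolates the time in which it would appear. SAP 7.7.1 lists 14 TEAE summaries, and none splits events by onset before or after the last dose. The only post-treatment category in SAP 7.7 is for deaths (7.7.2), and it starts after day 28.

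The laboratory point is separate and more mechanical. The visit window extends four days beyond the analysis cut-off, so a sample can be fully on schedule and still be left out of two of the main laboratory safety displays.

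At stake is whether a reader of the safety tables can see how many stoppers had hemolysis or anemia afterwards. No efficacy inference depends on it.

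**Working it through.** The plan gives no figure on this point to reproduce. The check is a comparison of definitions plus day counts.

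**1. Where post-stop events go.** The on-treatment period ends 28 days after the last dose, taper included (SAP 6.3.2, 6.3.5). Routine AE recording also ends 28 days after the last dose (Protocol 9.2.1). So routinely collected post-stop events do enter the TEAE tables. They are pooled with all earlier on-drug events.

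**2. What pooling hides.** A subject with on-drug anemia and a second anemia event after stopping adds nothing more to the any-grade count. A more severe second event does reach the worst-grade table, but is not marked as post-stop. Let p be the on-drug risk and q the post-stop risk, taken as independent. The table then prints p + q − pq. Both rates here are assumptions for illustration only, because the documents give none:
- p = 5%, q = 20%: 0.05 + 0.20 − 0.01 = 24%
- p = 20%, q = 5%: 0.20 + 0.05 − 0.01 = 24%
- q = 10% with p = 5%, 20% or 40%: 14.5%, 28% or 46%

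The first two profiles are opposite but print the same number.

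**3. How much of the period is taper or post-stop** (calendar shares, not event shares).
- Week 288 completer: the extension starts on Day 169. Week 288 is Day 2017, and adding 7 taper days and 28 post-dose days gives Day 2052. Length = 2052 − 169 + 1 = 1,884 days; 35/1,884 = 1.9%.
- Stopper at Week 12: (1 + 4)/(12 + 1 + 4) = 5/17 = 29%.

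**4. The Safety Follow-up window.** 28 ± 4 gives days 24 to 32 after the last dose, which is 9 days. Days 24 to 28 (5 days) are on-treatment. Days 29 to 32 (4 days) are not: 4/9 = 44% of permitted days. Actual visit days are unknown, so this is not a share of samples. Including the visit by its label, or moving the laboratory cut-off to day 32, would exclude 0 of the 9.

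**5. How many stoppers there might be.** In Phase 2, 19 of 20 subjects completed the Core Period (Protocol 2.1.2.3.2), so 1/20 = 5% stopped (Clopper-Pearson 95% CI 0.1% to 24.9%). Applying that rate here is an assumption.
- Double-blind, mitapivat: 114 × 0.05 = 5.7, about 6 (range 0 to 28)
- Double-blind, placebo: 57 × 0.05 = 2.9, about 3 (range 0 to 14)
- Entering the extension, if every completer does: 171 × 0.95 = 162 (range 128 to 171)

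With zero events among n stoppers, the one-sided 95% upper bound on risk is 1 − 0.05^(1/n):
- n = 6: 39%
- n = 81 (half of 162 with post-stop data): 3.6%
- n = 128: 2.3%
- n = 162: 1.8%

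A separate table would say little in the double-blind report, and could be informative in the extension addendum.

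**The case against.** The strongest reply is that the plan already captures the period.
- **TEAE coverage.** The tables run to the day on which routine AE collection ends. This stands. A reader might infer that no adverse event table covers the time after stopping, but the SAP definitions show the opposite. The shortfall is separate display, not coverage.
- **Unscheduled samples.** SAP 6.4.5 puts unscheduled laboratory values into the worst-grade summaries, so a sample drawn for suspected hemolysis within 28 days of stopping is included. Clinically significant results are also reported as AEs (Protocol 9.1.3). This stands.
- **Plots.** SAP 7.6.3.2 plans by-subject plots of hemolysis and erythropoiesis markers with transfusions and prescribed dose. They partly show what follows a stop. They are individual plots, though, and give no count.
- **Timing.** Protocol 2.1.2.1 gives an effective half-life of about 3 to 6 hours and, in healthy subjects, 2,3-DPG near baseline within 72 to 120 hours of a single dose. An acute event would probably come well before day 29. This limits the clinical weight of the day 29 to 32 gap, but does not explain leaving out an on-schedule safety sample.
- **By-visit summaries.** SAP 7.7.3 plans laboratory values by study visit, and Safety Follow-up is a scheduled visit. The SAP does not name that row, and SAP 7.7 limits safety summaries to on-treatment data. Whether a day 29 to 32 value would appear there is therefore unclear.
- **No withdrawal endpoint.** The visible objectives contain none, and the monitoring text is guidance to sites. A reader might infer that the SAP departs from the protocol. It does not: Protocol 10.4.1.2 and 10.4.4.1 use the same definitions.

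By-subject listings would also allow the post-stop count to be rebuilt by hand.

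**Conclusion.** The point holds in limited form. Post-stop adverse events through day 28 are tabulated but cannot be distinguished from on-drug events. An on-schedule Safety Follow-up sample on 4 of 9 permitted days falls outside the laboratory worst-grade and shift tables, even though SAP section 2 carries early stoppers' data to the end of safety follow-up in the primary report. The consequence lies mainly in the extension addendum, where Week 288 completers are told to taper and 1.9% of the period carries the information about stopping.

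This is a descriptive omission, worth correcting because correction is cheap. It does not show that a withdrawal signal would be lost, and 44% is not a proportion of samples lost. The pooled percentages rest on assumed rates and independence. The stopper counts rest on one stop among 20 Phase 2 subjects. SAP 7.11 is not in the public text, so a relevant summary there cannot be ruled out.

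**What to change.** Keep the existing tables and baselines.

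(a) In SAP 7.7.1 add one descriptive TEAE table, by SOC and PT and by arm, of events with onset from the day after the last dose through day 28. The denominator is subjects who stopped study drug, including Week 288 completers and any Week 24 completers who do not enter the extension. Show taper-period onsets separately only if the Prescribed Dose eCRF identifies a taper. A taper uses the same 100 mg QD dose as the reductions in Protocol Tables 6 and 7, so this has to be checked first.

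(b) In SAP 7.7.3 include the Safety Follow-up sample by nominal visit through day 32, as a stated exception to the day-28 cut-off. Apply this to the by-visit summaries and preferably to the worst-grade and shift tables. Report Hb, LDH, indirect bilirubin and reticulocytes, all of which are already collected at that visit.

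The cost is SAP wording and a little more analysis work. There are no new visits and no alpha is spent. The limits should be stated: few stoppers in the double-blind report, no placebo comparator in the extension, and one scheduled sample near day 28 that can miss an acute event.
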